11.6.2 Laboratory Data

Routine safety clinical laboratory tests (biochemistry, hematology, coagulation, urinalysis) will be carried out at:

Part A: Screening, Day -1, 24h post dose, 72h post dose and at follow-up. An additional urinalysis test will be carried out at Day 1, 12h.

Part B: Screening, Day -1, 24h post dose, 72h post dose and at follow-up. An additional biochemistry test will be carried out at Day 1 pre dose (total serum testosterone only) and an additional urinalysis test will be carried out at Day 1 – 12h.

Part C: Screening, Day -1, 24h post dose, 72h post dose, pre-dose on Day 5 and at follow-up. An additional biochemistry test (total serum testosterone and LH only) will be carried out at Day 1 pre-dose, Day 5, Day 8 and Day 11 and an additional urinalysis test will be carried out at Day 1, 12h.

The laboratory parameters required for this study are listed in section 9.2.1.

Laboratory data listings will be presented in two ways:

- Out of range values - any values that fall outside of the normal/alert ranges based on the reference ranges provided by the Simbec-Orion Laboratory Services (presented in listing format within the data summaries)
- All safety laboratory data (including physician's review (Normal, Abnormal-NCS, Abnormal-CS)) with any out of range values flagged (presented within the data listings).

Descriptive statistics (N, n, mean, SD, minimum, median and maximum) of absolute and change from baseline (last assessment prior to first dose within a treatment period) values for each parameter at each protocol defined time point will be tabulated by treatment.

Microscopy, virology, COVID-19 test, urine drugs of abuse and alcohol screen and any unplanned laboratory parameters will also be listed.

If there are no further parameters databased other than those specified in section 9.2.1 then the 'Other Laboratory Data' listings should display, 'No other laboratory parameters to report'.

Laboratory data will be listed and summarised using the Safety Set.

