8.5 Toxicology

In rats the maximum tolerated dose (MTD) following three consecutive days of oral administration of AX-158 was determined to be 300 mg/kg/day. A subsequent dose range finding study was conducted with doses up to 180 mg/kg/day for 14 days whereby the MTD was determined to be 180 mg/kg. A 28-day GLP toxicity study was carried out with doses up to 180 mg/kg/day by oral route. The studies elicited a decrease in the size of testes, epididymides, seminal vesicles and coagulating glands at doses \geq 50 mg/kg/day. The changes in testes and epididymides were microscopically associated with degeneration/atrophy of seminiferous tubules of testes and cell debris/decreased sperm in lumen of epididymides. However, there were no associated microscopic changes in seminal vesicles and coagulating glands. These changes were observed to be partially reversible in recovery animals. Test item related perivascular inflammation at the base of heart involving the tunica adventitia of aorta and surrounding brown adipose tissue was noted at \geq 50 mg/kg/day in both sexes and a single incidence in recovery group female animal. Chronic inflammation was observed with the presence of mononuclear cells and fibroblasts. The NOAEL in rat in the 28-day study was 15 mg/kg/day.

In minipigs, a MTD study achieving doses up to 600 mg/kg was performed by oral route. The MTD was $>$ 600 mg/kg. A 14 days DRF study was subsequently performed at 300 and 600 mg/kg. The MTD following 14 consecutive days of oral administration was considered to be

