Visits ^{1,2}	Screening	Treatment Periods 1 & 2														Follow up	
		In-house															
Days	Day - 28 to -2	Day - 1	Day 1										Post-Treatment 1 (Day 2)	Post-Treatment 2 (Day 3)	Post-Treatment 3 (Day 4)	5-7 days from last IMP dose	
Time (h)			Pre-Dose	0	0.5	0.75	1h	2h	3h	4h	6h	8h	12h	24h	36h	48h	72h
Informed Consent	X																
Inclusion/Exclusion ³	X	X	X														
Demographics	X																
Height/Weight/BMI ⁴	X	X															
Medical History & Concurrent Conditions		X															
Virology Tests (HIV, HBsAg, HCV)		X															
Drug and Alcohol Screen ⁵	X	X															
COVID-19 Test		X															
Biochemistry	X ⁶	X	X ⁶										X		X		X
Haematology	X	X											X		X		X
Urinalysis	X	X											X		X		X
Coagulation ⁷	X	X											X		X		X
Randomisation			X														
Adverse Events	X	X	X	X	X	X	X	X	X	X	X	X	X	X	X	X	X
Vital Signs ⁸	X	X	X		X	X	X	X	X	X	X	X	X	X	X	X	X
Physical Examination		X ¹¹													X ¹¹		X ¹¹
12-Lead ECG ⁹	X	X	X		X								X	X		X	X
Prior & Concomitant Medication	X	X	X	X	X	X	X	X	X	X	X	X	X	X	X	X	X
Dose IMP ¹⁰			X														
Blood Sampling for PK			X	X	X	X	X	X	X	X	X	X	X	X	X	X	

1. All cohorts will complete Treatment Period 1 & 2.
2. For Treatment Periods 1 & 2, participants will be in the clinical unit for their in-house period from the morning before dosing (Day -1), until the completion of all the assessments on Post-Treatment 3 (Day 4).
3. Eligibility will be determined during screening. Continued eligibility will be confirmed on Day -1, and pre-dose Day 1 for Treatment Periods 1 & 2.
4. Height measured at Screening only.
5. A urine sample will be used to screen for drugs of abuse (including alcohol and cotinine).
6. Total serum testosterone required at screening and pre-dose D1 each treatment period (Biochemistry sample: pre-dose Day 1 total serum testosterone only).
7. Coagulation testing INR, APTT and PT.
8. Vital signs include the following assessments: supine systolic and diastolic blood pressure, supine heart rate, respiration rate and oral temperature
9. 12-lead ECG will be performed at screening, each period pre-dose and at 30 min, 4 h, 12 h, 24 h, 48 h and 72 h post-dose and at the post-study follow up visit.
10. Participants will receive a single dose of AX-158 following an overnight fast of at least 10 h OR following consumption of a high-fat breakfast over 2 treatment periods (1 per period). AX-158 should be administered 30 mins after the start of the meal.
11. Symptom directed

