5 DEFINITIONS AND DERIVED VARIABLES

Treatment/IMP: Treatment or IMP is taken to mean either AX-158 at all dose levels, in the fed or fasted state, or placebo.

Baseline: For Part A and Part C unless stated otherwise, baseline is defined by subject and by variable as the last non-missing value (including repeat/unscheduled assessments) before the first dose of study drug.

For Part B unless stated otherwise, baseline is defined by subject and by variable as the last non-missing value (including repeat/unscheduled assessments) before the first dose of study drug in each treatment period. This will normally be the pre-dose assessment on Day 1 of each treatment period but if this assessment is missing (or not planned) then the last assessment prior to first dose in Period 1 will be used instead, if available. Specific baselines for each endpoint are defined in Section 11, where appropriate.

Study Day: Study day is the number of days since start of treatment where the date of first dose is counted as Day 1.

Blood Sampling Time Deviation: Actual sample time – planned sample time.

Protocol Deviation: a deviation related to study inclusion or exclusion criteria, conduct of the trial, subject management or subject assessment. This refers to any change, divergence, or departure from the study design or procedures defined in the protocol. Protocol deviations captured in the CRF will be discussed at the Data Review Meeting (DRM) before Database Lock (DBL). In addition, any deviations

identified during the DRM will be discussed and included in the database as necessary. All protocol deviations within the study database will be classified as either 'Major' or 'Minor' prior to DBL, details of which will be included within the Protocol Deviations listing.

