9.2 EXTERNAL DATA

9.2.1 Laboratory Data

Transfers of safety laboratory data will be provided by Simbec-Orion Laboratory Services, delivered to Simbec-Orion Data Management via electronic transfer and stored within the study database and subsequently, within the appropriate SDTM and ADaM domains.. Details of laboratory data are documented in the Data Management Plan (DMP). Populated test transfers will be received before programming can start.

The following results will be included:

- **Hematology:** Hemoglobin, hematocrit, mean corpuscular volume, mean corpuscular hemoglobin, mean corpuscular hemoglobin concentration, platelet count, red blood cell count, red blood cell distribution width, white blood cell count and WBC differential count (neutrophils, lymphocytes, monocytes, eosinophils, and basophils) (reported in absolute and percentage values).
- **Biochemistry:** Alanine transaminase, albumin, alkaline phosphatase, aspartate transaminase, bicarbonate, total bilirubin, direct bilirubin (if total bilirubin is raised), calcium, chloride, c-reactive protein, creatine kinase, creatinine, glucose (random), gamma glutamyltransferase, potassium, total protein, sodium, urea, total serum testosterone and luteinizing hormone.
- **Urinalysis:** Bilirubin, blood, glucose, ketones [or ketone bodies], leucocytes, nitrite, pH, protein, specific gravity, and urobilinogen.
- **Coagulation:** International normalized ratio, Activated partial thromboplastin time and prothrombin time.
- **Microscopy:** In the event that the urinalysis 'dipstick' test result is positive for nitrite and/or 2+ or more reported for protein, blood, and/or leucocytes, the following test parameters will be reported microscopically: bacteria, casts (non-pathogenic), casts (pathogenic), crystals, epithelial cells, red blood cells and white blood cells
- **Virology:** HBsAg, HCV Ab and HIV test (antibodies to HIV-1 and HIV-2).
- **COVID-19 Test:** A nasopharyngeal and/or oropharyngeal swab will be collected. COVID-19 testing will be routinely performed via lateral flow test (LFT) however, a RT-PCR test may be performed at the PI's discretion.
- **Drugs of Abuse Screen and Alcohol:** alcohol, amphetamines, barbiturates, benzodiazepines, cannabinoids/tetrahydrocannabinoids (THC), cocaine, cotinine, methadone, and opiates.

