10 STATISTICAL METHODS

10.1 GENERAL PRINCIPLES

- All statistical methods will be based on the International Conference on Harmonisation (ICH) E9 document “Statistical Principles for Clinical Trials”.
- All data collected will be presented within data listings.
- Generally, for Part A and Part C, data listings will be sorted by subject, visit and treatment, with the exception of baseline data listings which will be sorted by treatment, subject and visit.
- Generally, for Parts A and C, data listings will be sorted by part, cohort, treatment, subject, visit/time point. Generally, for Part B, data listings will be sorted by part, subject, visit and treatment, where appropriate.
- Generally, data will be summarised by treatment for each part separately. Where appropriate, a summary of all active treatments (Parts A and C) and treatments overall will be included. For Part B, baseline data will be summarised overall. The format of the summaries is defined in the shells at the end of this document.
- Repeated visits will be denoted with ‘RPT’. Unscheduled visits will be denoted with ‘UNS’.
- In summary and analysis tables of continuous variables, standard descriptive statistics (N [number within analysis set, or group, or subgroup], n [number of observations included in analysis], mean, standard deviation [SD], median, minimum and maximum) will be presented. Least squares means (LSMean) and 90/95% confidence intervals (CI) will be presented in the statistical analysis outputs as appropriate. For PK summaries, geometric mean and coefficient of variation (%CV) will also be used to summarise the data.
- Unless otherwise specified, the minimum and maximum statistics will be presented in summary tables to the same number of decimal places as the original data. The mean, median, LSMean, and CI will be presented to one more decimal place than the original data. SD will be presented to two more decimal places than the original data.
- Derived PK parameters and concentration data listings and summaries will be presented to 3 significant figures (with the exception of CV%, which will be presented to 1 decimal place). The

ratio of the geometric LSMeans (i.e. test/reference) and its associated confidence interval will be presented to 2 decimal places.

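### Part B testosterone: the only scheduled value after an AX-158 dose is defined as the Period 2 baseline, so no planned summary isolates the change after exposure

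*SAP*

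**What the plan says.** **Schedule.** Footnote 6 to the Part B flow chart (SAP Section 3.4.1) reads "Total serum testosterone required at screening and pre-dose D1 each treatment period" and marks the Day 1 sample as testosterone only. SAP Section 11.6.2 describes the same extra Day 1 pre-dose test. SAP Section 9.2.1 ends the biochemistry panel with "total serum testosterone and luteinizing hormone" and sets no visit limits there, so the restriction comes from the footnote and Section 11.6.2.

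**Protocol version.** The protocol supplied (V4.0) has Part B testosterone at screening only (Table 10.9.2, footnote 6). The SAP was written from V5.0, which is not among the documents.

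**Baseline.** SAP Section 5 resets the Part B baseline before the dose in each period and adds: "This will normally be the pre-dose assessment on Day 1 of each treatment period". Section 11.6.2 applies this to laboratory data: "change from baseline (last assessment prior to first dose within a treatment period) values for each parameter at each protocol defined time point".

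**Tabulation.** SAP Section 10.1: "Generally, data will be summarised by treatment for each part separately". The Part A shell for Table 14.3.2.5 has blocks by treatment and rows by visit, and is to be reused for Part B with suitable visits.

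**Design.** Part B is a two-sequence crossover in up to 8 participants (SAP Sections 3.1 and 3.6), with at least 7 days between doses (Protocol Section 10.1).

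**The concern.** Resetting the baseline in each period is reasonable for parameters measured both before and after each dose. It does not suit a parameter measured only before dosing. Here the one post-exposure value becomes a reference point with nothing to compare against it, and summarising by treatment rather than by period can blend it with unexposed values.

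The parameter is tied to a named nonclinical risk. Protocol Section 8.5 reports in rats a "decrease in the size of testes, epididymides, seminal vesicles and coagulating glands at doses" of 50 mg/kg/day and above, and says a treatment-related testicular effect in minipigs cannot be ruled out. Part A takes testosterone at screening only, so the Part B Period 2 pre-dose sample is the only scheduled testosterone value after a single dose anywhere in the study. Part C does not share the problem: it has one baseline, with values during and after dosing to compare against it.

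**Working it through.** The plan states no figure on this point, so there is none to reproduce.

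**Step 1: which values can form a change.**

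| Part B testosterone value | After an AX-158 dose? | Role under SAP Sections 5 and 11.6.2 | Later value in the same period |
|---|---|---|---|
| Screening | No | Before baseline | – |
| Period 1 Day 1 pre-dose | No | Period 1 baseline | None scheduled |
| Period 2 Day 1 pre-dose | Yes, at least 7 days after the Period 1 dose | Period 2 baseline | None scheduled |

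The number of participants with a change from a pre-exposure baseline is 0 of 8.

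**Step 2: what the absolute summaries show if the two periods share one row.** Let n_A participants be dosed fasted then fed, n_B fed then fasted, and n = n_A + n_B. Let μ be the unexposed mean, and d_fast and d_fed the shifts still present at Period 2 pre-dose after a fasted or fed Period 1 dose.

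- Fed block: n_B unexposed values and n_A values taken after a *fasted* dose. Mean = μ + n_A·d_fast/n.
- Fasted block: n_A unexposed values and n_B values taken after a *fed* dose. Mean = μ + n_B·d_fed/n.
- Fed minus fasted = (n_A·d_fast − n_B·d_fed)/n.
- Within-participant Period 2 minus Period 1 = (n_A·d_fast + n_B·d_fed)/n.

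The sequence split is not stated, so several are shown. Shifts are in units of d_fast.

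| n_A : n_B | d_fed / d_fast | Fed block shift | Fasted block shift | Fed minus fasted | Paired change |
|---|---|---|---|---|---|
| 4:4 | 1 | 0.50 | 0.50 | 0 | 1.00 |
| 5:3 | 1 | 0.625 | 0.375 | 0.25 | 1.00 |
| 6:2 | 1 | 0.75 | 0.25 | 0.50 | 1.00 |
| 4:3 | 1 | 0.571 | 0.429 | 0.143 | 1.00 |
| 4:4 | 1.5 | 0.50 | 0.75 | −0.25 | 1.25 |
| 4:4 | 2 | 0.50 | 1.00 | −0.50 | 1.50 |

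As an illustration, assume a 4:4 split and a 30% fall in everyone (not a figure from the documents). Each block mean is (4 × 1 + 4 × 0.70)/8 = 0.85 of the unexposed mean, and the blocks differ by 0. The paired change is 0.70 − 1 = −0.30.

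**Step 3: if the visit label carries the period.** The rows then separate. Each participant receives the fed dose in only one period, so the Period 1 and Period 2 rows within one treatment block come from different people. A within-participant change is still not tabulated.

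**Step 4: precision of the paired change.** Half-width of the 95% CI = t(0.975, n−1) × SD of the paired difference / √n, which is 0.84, 0.92 and 1.05 times that SD for n = 8, 7 and 6. Taking the SD as √2 × within-subject CV, n = 8 gives 0.836 × 1.414 × CV = 1.18 × CV. The documents give no CV; over an assumed range:

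| Assumed CV | 10% | 15% | 20% | 25% |
|---|---|---|---|---|
| Half-width (percentage points) | 11.8 | 17.7 | 23.6 | 29.6 |

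**The case against.** **The fall is not hidden.** A reader might infer that any drug effect cancels between fed and fasted, or that the SAP cannot show a fall at all. The documents support neither. Exact cancellation needs equal sequences, which are not stated, and an effect that does not depend on food, which is the factor Part B varies. Even with cancellation, half of a common shift stays in each block's absolute mean, alongside a screening row. Listing 16.2.8.1 gives every individual value, and the Part B out-of-range table (Table 14.3.2.1) has a study period column. With at most 8 participants the pairs can be read by eye. This stands, and limits the point to a missing summary.

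**The shell is generic.** The rows of Table 14.3.2.5 are visit placeholders drawn for Part A, and SAP Section 15 allows layouts to change. Whether the two periods share a row is therefore inferred. This stands too. The empty change from baseline does not depend on it: it follows from Sections 5 and 11.6.2 and the schedule.

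**The sample may be for eligibility.** Inclusion criterion 8 concerns testosterone, eligibility is reconfirmed before dosing in each period, and protocol V5.0 is not available to settle the purpose. That is possible, but the SAP still puts laboratory parameters among its primary safety variables and summarises them.

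**The stakes are modest.** The primary objective names Parts A and C. The rat findings came from repeated dosing, whereas Part B gives two single doses (15 mg in the SAP shells). Part C has placebo controls, testosterone and LH. The Period 2 sample can show only what persists at least 7 days after one dose. These points lower the priority without removing the mismatch.

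**Conclusion.** The concern holds in a limited form. Under the SAP schedule, the only Part B testosterone value taken after exposure is used as a baseline, and no participant gets a change from a pre-exposure value. If the two periods share a row, a shift common to both conditions appears at about half size in each block and cancels between blocks when the sequences are equal. With unequal sequences or a food-dependent effect, a residual remains under the wrong label, because the fed block holds the after-effect of the fasted dose and the fasted block that of the fed dose. The data stay recoverable from the listings, but no planned summary isolates the change.

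This rests on reading the schedule footnote and Section 11.6.2 as limiting testosterone to the stated visits. If it were run at every biochemistry visit, as the unrestricted panel in Section 9.2.1 could be read, later values would exist in each period and the change columns would not be empty. The 4:4 split, the 30% fall and the CV range are assumptions.

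**What to change.** In SAP Sections 5 and 11.6.2, except Part B testosterone from the per-period baseline and use the Period 1 Day 1 pre-dose value as baseline for both periods. In the Part B version of Table 14.3.2.5, add a block with the Period 1 and Period 2 pre-dose values and the within-participant Period 2 minus Period 1 change and percent change, overall and by sequence. State in the same place that testosterone is measured only at the visits in the schedule footnote.

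The cost is one or two SAP sentences and one table block, from samples already planned; no assessment or clinical rule changes. The summary would be descriptive only, without a placebo comparator. At the precision shown above, it could reveal a large persistent shift but not a small one.

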11.6.3 Vital Signs

Vital Signs will be recorded at:

Part A: Screening, Day -1, Day 1 pre-dose, 30 mins, 45 mins, 1h, 2h, 3h, 4h, 6h, 8h, 12h, 24h post dose, 36h post dose, 48h post dose, 72h post dose and follow-up.

Part B: Screening, Day -1, Day 1 pre-dose, 30 mins, 45 mins, 1h, 2h, 3h, 4h, 6h, 8h, 12h, 24h post dose, 36h post dose, 48h post dose, 72h post dose and follow-up.

Part C: Screening, Day -1, Day 1 and Day 10 at pre-dose, 30 mins, 45 mins, 1h, 2h, 3h, 4h, 6h, 8h, 12h, 24h post dose, 36h post dose, 48h post dose, 72h post dose, pre-dose on Day 5 and follow-up.

A window of \pm 10 min in relation to the nominal time-point is allowed.

Vital signs parameters (supine systolic and diastolic blood pressure and pulse rate, oral temperature and respiratory rate) will be listed with any out of normal range values (see Appendix 16.1) flagged (flag appended to relevant result). Descriptive statistics (N, n, mean, SD, minimum, median and maximum) of absolute and change from baseline (Day 1, pre-dose [of each treatment period for Part B] or last assessment prior to first dose, as applicable) values at each time point will be tabulated by treatment.

Vitals signs data will be listed and summarised using the Safety Set.

11.6.4 Electrocardiogram

12-lead ECGs will be performed at:

Part A: Screening, Day -1, Day 1 pre-dose, 30 min, 4h, 12h, 24h post dose, 48h post dose, 72h post dose, follow-up.

Part B: Screening, Day -1, Day 1 pre-dose, 30 min, 4h, 12h, 24h post dose, 48h post dose, 72h post dose, follow up.

Part C: Screening, Day -1, Day 1 and Day 10 at pre-dose, 30 min, 4h, 12h, 24h, 48h, and 72h post dose, pre-dose on Day 5 and follow-up.

A window of \pm 10 min in relation to the nominal time-point is allowed.

12-lead ECG parameters (heart rate, PR interval, QRS width, QT interval and QT interval corrected using Fridericia's formula (QTcF)) will be listed with any out of normal range values (see Appendix 16.1) flagged (flag appended to relevant result). Descriptive statistics (N, n, mean, SD, minimum, median and

maximum) of absolute and change from baseline (Day 1, pre-dose [of each treatment period for Part B] or last assessment prior to first dose, as applicable) values at each time point will be summarised by treatment.

In addition, frequencies for QTcF data will be calculated and summarised according to the following categories:

For absolute values:

- QTc \leq 450 msec
- 450 < QTc \leq 480 msec
- 480 < QTc \leq 500 msec
- QTc > 500 msec.

For change from baseline:

- Decreased/No Change
- QTc increase \leq 30 msec
- 30 < QTc increase \leq 60 msec
- QTc increase > 60 msec

ECG data will be listed and summarised using the Safety Set.

